## 1.0 SYNOPSIS

Name of the Sponsor:	Individual Study Table Referring to Part of the Dossier:	For National Authority Use Only
ProQR Therapeutics	Volume: NA Page: NA	
Name of Study Drug: QR-110 Solution for Intravitreal Injection		
Name of Active Ingredient: QR-110		
Title of Study:	An Open-Label, Multiple Dose, Dose Escalation Study to Evaluate the Safety and Tolerability of QR-110 in Subjects with Leber's Congenital Amaurosis (LCA) due to c.2991+1655A>G Mutation (p.Cys998X) in the CEP290 Gene	
Study Centers:	Participation of approximately 3 study centers planned	
Phase of Development:	Phase 1b/2	
Study Period:	Anticipated to be approximately 18 months	
Duration of Subject Participation:	13 months (Screening 28 days; study period 12 months)	
Rationale:	
Leber's congenital amaurosis (LCA) is a severe inherited retinal degenerative disease resulting in blindness, often in early childhood. In subjects with LCA due to the p.Cys998X mutation in Centrosomal Protein of 290 kDa (CEP290), visual symptoms are usually detectable before 1 year of age and further deterioration over time has also been reported (den Hollander 2008, Yzer 2012). Patients show severe vision disturbances from an early age and slow progressive loss of remaining vision (Cideciyan 2007, Cideciyan 2011). There are currently no approved therapies for the treatment of LCA due to the p.Cys998X mutation in CEP290 (subsequently referred to as the CEP290 p.Cys998X mutation) and a large unmet medical need exists.
 
The CEP290 p.Cys998X mutation results in aberrant splicing of CEP290 with mutant messenger ribonucleic acid (mRNA) and truncated protein production in affected individuals. QR-110 is a single stranded, chemically modified, RNA oligonucleotide that is designed to correct aberrant splicing in CEP290 gene, enabling production of fully functional RNA and protein.
	
Objectives:	
Primary: To evaluate the safety and tolerability of QR-110 administered via intravitreal (IVT) injection in subjects with LCA due to the CEP290 p.Cys998X mutation
 
Secondary: To evaluate the serum pharmacokinetics of QR-110 administered by IVT injection in subjects with LCA due to the CEP290 p.Cys998X mutation
 
To evaluate the efficacy of QR-110 administered by IVT injection in subjects with LCA due to the CEP290 p.Cys998X mutation
	
Number of Subjects (planned):	12	
The final number of subjects is dependent on whether any dose levels are expanded by the Data Monitoring Committee (DMC) and Sponsor Medical Monitor.

Study Design	The first-in-human study of QR-110 will be an open-label, multiple dose, dose escalation study to evaluate the safety and tolerability of QR-110 administered via IVT injection in subjects with LCA due to the CEP290 p.Cys998X mutation. Subjects will	

	
be assigned to receive a specified dose level of QR-110 (loading dose and maintenance dose) and will receive that dose throughout their participation, while they are monitored for safety. No intrasubject dose escalation is planned. Up to 3 dose levels of QR-110 will be evaluated. Dose escalation decisions and initiation of dosing in pediatric subjects (6 to <18 years of age) will be determined by the DMC and Sponsor Medical Monitor review of safety and tolerability data. The DMC and Sponsor Medical Monitor will also review all available safety data at key study time points (eg, prior to the first subject in the first adult cohort (Cohort A1) receiving each subsequent dose of study drug).
 
QR-110 will be administered by unilateral IVT injection. Each subject will receive up to 4 doses of QR-110 in their worse eye (as defined by visual acuity at Screening, subsequently referred to as treatment eye) every 3 months and will be assessed for safety and tolerability at follow up visits. If both eyes have the same visual acuity, the Investigator should determine the eye with the worse visual function as the treatment eye, according to other measures of ophthalmic function (Full-field Stimulus Testing [FST] or mobility course score). If the visual function is the same per the Investigator's assessment, then the treatment eye will be determined at Investigator discretion. No placebo nor sham injections will be administered in the contralateral eye.
 
The contralateral eye and the subject's own baseline measurements will serve as controls.
 
Subjects who do not meet stopping criteria prior to their next scheduled injection will receive their planned dose (Section 4.2.2). Subjects who meet stopping criteria will be discontinued from dosing and will be followed for safety and efficacy.
 
The DMC and/or Sponsor Medical Monitor may decide to de-escalate the dose, hold the dose (delay or skip), or discontinue study drug for an individual subject, in consultation with the Investigator. Subjects who discontinue study drug will continue to be followed for safety and efficacy.
 
An extension study, which would permit continued dosing of eligible subjects who complete PQ-110-001, is planned.
 
Dose Escalation
 
Specifics of the dose escalation plan are described in detail in Section 4.2.1.5. It is planned to dose at least 2 adults and, subsequently, at least 2 pediatric subjects at each dose level of QR-110. Up to 3 dose levels are planned across 3 dose cohorts. No intrasubject dose escalation will occur. Dosing will be staggered such that:
 

• The first 2 subjects at any dose level will be dosed at least 2 weeks apart

• At least 4 weeks of post dose safety and tolerability data on the previous cohort will be reviewed by the DMC and Sponsor Medical Monitor prior to dose escalation in subsequent subjects

• Dosing and dose escalation of pediatric cohorts will be initiated following DMC and Sponsor Medical Monitor review and will follow that of the corresponding adult cohort by at least 4 weeks

 
Following DMC and Sponsor Medical Monitor review and decision on dose escalation, the first subject at the next dose level may be dosed and the second subject at that dose level may be dosed 2 weeks later. Safety and tolerability data, including follow-up for at least 4 weeks post dose, will be reviewed by the DMC and Sponsor Medical Monitor. A complete discussion of the rules regarding timing of doses for individual subjects is presented in Section 4.2.1.5.
 
Pediatric subjects will only receive a given dose level of QR-110 following DMC and Sponsor Medical Monitor acceptance of at least 4 weeks of post dose safety and

--	--

	
tolerability data in the 2 adults at that same dose level. Therefore, dosing of pediatric subjects will remain a minimum of 4 weeks behind dosing of the corresponding adult cohort at the same dose level. The safety measures around the timing of dosing and dose escalation of adult subjects also apply to pediatric subjects. The first 2 pediatric subjects at each dose level will be dosed at least 2 weeks apart. At least 4 weeks of safety and tolerability data for the first 2 pediatric subjects at each dose level will be reviewed by the DMC and Sponsor Medical Monitor prior to enrollment and dose escalation of subsequent pediatric subjects.
 
Safety review will be conducted by the DMC and Sponsor Medical Monitor before each cohort initiation and on an ad hoc basis as needed. The Sponsor will also perform safety review on an ongoing basis.
 
Study Plan
 
The study includes a 28-day screening period.
 
During the screening period, subjects will be assessed according to the eligibility criteria. Historic genotyping results from a certified genetic laboratory are acceptable with Sponsor approval. For subjects without a historic genotyping result, genotyping and gene sequencing analysis to determine the presence of the CEP290 p.Cys998X mutation will be performed. It is recommended that screening be conducted in a stepwise manner, so that eligibility is confirmed first with less intensive assessments and more intensive assessments are conducted after eligibility by all other criteria have been confirmed.
 
Most measures of visual function (Best-corrected Visual Acuity [BCVA], FST mobility course, oculomotor instability and Pupillary Light Reflex [PLR]) will be measured a minimum of 2 times prior to the subject's first dose of study drug to evaluate intrasubject variability (Screening and predose on Day 1). Measures of retinal anatomy (infrared imaging, and Optical Coherence Tomography [OCT]) and electroretinogram (ERG) will be measured a minimum of 1 time prior to the subject's first dose of study drug. Any predose assessment may be repeated if the results are considered unreliable or of unacceptable quality by the Investigator or if the assessment could not be completed. In the case of repeat assessments, the measure reflecting the average of the measures will be considered the Baseline value.
 
Subjects who meet all eligibility criteria will be enrolled into the study and will receive their first dose of study drug on Day 1. QR-110 will be administered via IVT injection into the subject's treatment eye in accordance with the procedures outlined by the American Academy of Ophthalmology (Avery 2014).
 
Subjects will be monitored clinically for increases in intraocular pressure (IOP) and signs of inflammation and endophthalmitis during the post-injection period.
 
Subjects will be evaluated the day after each administration of study drug for safety monitoring (all doses) and to enable collection of serum samples for pharmacokinetic (PK) analysis
 
Subjects will return to the study center to complete safety assessments at 7 days, and 1 month, 2 months (doses 1 and 2 only) and 3 months post dose. In addition, subjects will be evaluated by telephone interview at 14 days post dose for the first dose only. Efficacy assessments, including retinal imaging, functional assessments of vision,
 
All assessments will be performed on both the treatment and contralateral eyes.

--	---

	
The Investigator, Sponsor Medical Monitor and/or the DMC may decide to stop treatment for an individual subject due to an adverse event (AE). Stopping criteria are described in Section 4.2.2.

Diagnosis and Main Criteria for Eligibility:	
Inclusion Criteria:
 
 
1. Male or female, <math>\geq</math> 6 years of age at Screening with a clinical diagnosis of LCA and a molecular diagnosis of homozygosity or compound heterozygosity for the CEP290 p.Cys998X mutation, based on genotyping analysis at Screening. Historic genotyping results from a certified laboratory are acceptable with Sponsor approval.
 
2. Best-corrected visual acuity greater than or equal to light perception in both eyes and equal to or worse than Logarithm of the Minimum Angle of Resolution (LogMAR) + 0.6 (Snellen notation 20/80) in the worse eye and equal to or worse than LogMAR + 0.4 (Snellen notation 20/50) in the contralateral eye.
 
3. Detectable outer nuclear layer (ONL) in the area of the macula in the opinion of the Investigator, as determined by OCT
 
4. An ERG result consistent with LCA, as determined by the Investigator and the Reading Center. A historic ERG result is acceptable for eligibility.
 
5. Clear ocular media and adequate pupillary dilation to permit good quality retinal imaging, as assessed by the Investigator
 
6. An adult (<math>\geq</math> 18 years) willing and able to provide informed consent for participation -OR- a minor (6 to <math><</math> 18 years) with a parent or legal guardian willing and able to provide written permission for the subject's participation prior to performing any study related procedures and pediatric subjects able to provide age appropriate assent for study participation
 
7. An adult willing to comply with the protocol, follow study instructions, attend study visits as required and willing and able to complete all study assessments, in the opinion of the Investigator -OR- a minor able to complete all study assessments and comply with the protocol and has a parent or caregiver willing and able to follow study instructions and attend study visits with the subject as required, in the opinion of the Investigator
 
8. Female subjects of childbearing potential, who have reached menarche, and male subjects must be sexually inactive by abstinence, which is consistent with the preferred and usual lifestyle of the subject, or agree to use adequate birth control, as defined in Section 6.2.3. Women of non-childbearing potential may be included without the use of adequate birth control, provided they meet the criteria in Section 6.2.3.
 
9. Adequate verbal communication as to allow assessment via mobility course, in the opinion of the Investigator
 
 
No waivers to the inclusion criteria are permitted.
 
Exclusion Criteria:
 
 
1. Diagnosed with an inherited retinal degenerative disease other than LCA or diagnosed with LCA due to a mutation in CEP290 which does not include at least one copy of p.Cys998X, either in homozygosity or compound heterozygosity. Note: The confirmed presence of known disease causing mutations in other genes involved in retinal dystrophy is exclusionary.
 
2. Syndromic disease such as Alström syndrome, Batten disease, Joubert syndrome, peroxisomal diseases and Senior-Løken syndrome or other disease with similar presentation
 


	

3. Any contraindication to IVT injection according to the Investigator's clinical judgment and international guidelines (Avery 2014)

4. Pregnant or breast-feeding female

5. Any clinically significant cardiac disease or defect, in the opinion of the Investigator

6. Personal or family history of prolonged QT syndrome or QTcF <math>\geq</math> 450 ms (adult subjects and pediatric subjects <math>>10</math> years old) or QTcB <math>\geq</math> 450 ms (pediatric subjects <math>\leq 10</math> years old) by electrocardiogram (ECG) at Screening

 
NOTE: Exclusion criteria 7 through 9 are related to acceptable laboratory values at Screening. Subjects with a screening laboratory value outside of the specified range may be permitted if the value is not clinically significant in the opinion of the Investigator, with concurrence from the Sponsor's Medical Monitor.
 

7. Estimated Glomerular Filtration Rate (eGFR) less than the lower limit of normal

8. Aspartate Aminotransferase (AST) or Alanine Aminotransferase (ALT) greater than 1.2x the upper limit of normal

9. One or more coagulation parameters (platelet count, International Normalized Ratio [INR]) outside of the normal range

10. Any ocular disease or condition that could compromise treatment safety, visual acuity or interfere with assessment of efficacy and safety, as determined by the Investigator

11. Prior receipt of intraocular surgery or IVT injection within 3 months prior to study start or planned intraocular surgery or procedure during the course of the study

12. Use of any investigational drug or device within 90 days or 5 half-lives of Day 1, whichever is longer, or plans to participate in another study of a drug or device during the PQ-110-001 study period

13. Any prior receipt of genetic therapy for LCA

14. Any severe, acute or chronic medical or psychiatric condition, including substance abuse, laboratory abnormality or other condition that, in the judgment of the Investigator, would place the subject at undue risk, interfere with the results of the study, or make the subject otherwise unsuitable

15. History of malignancy within 5 years prior to Screening, except adequately treated cutaneous squamous or basal cell carcinoma

 
No waivers to the exclusion criteria are permitted.

--	--

Endpoints:	
Primary
 

Frequency and severity of ocular AEs in the treatment and contralateral eyes

 
Secondary
 

Frequency and severity of non-ocular AEs

Changes in ophthalmic examination findings

Change in BCVA

Changes in infrared imaging

Changes in OCT findings

Changes in safety parameters, including vital sign measurements, physical examination findings, ECG and laboratory parameters

Characterize the PK profile of QR-110 in serum

Change in light sensitivity to red FST

Change in light sensitivity to blue FST

Change in amplitude to white PLR

Change in latency to white PLR

 
Exploratory

Study Drug, Dosage and Mode of Administration:	QR-110 Solution for IVT Injection, Up to 3 dose levels will be tested (loading dose/maintenance dose): 160 µg/80 µg, 320 µg/160 µg, and 500 µg/270 µg. QR-110 will be administered every 3 months for a total of 4 doses per subject.
Duration of Treatment:	12 months
Reference Therapy, Dosage and Mode of Administration:	Not applicable

Criteria for Evaluation:	
Safety and Tolerability:	

• Frequency and severity of ocular and non-ocular AEs

• Ophthalmic examination findings

• BCVA

• Infrared imaging

• OCT

• Vital sign measurements

• Physical examination findings

• ECG

• Laboratory parameters

PK:	

• Subjects will provide blood samples for presence of QR-110 at multiple time points

Efficacy:	

• BCVA

• White PLR

• Red FST

• Blue FST

Statistical Methods:	
Baseline demographics and disease characteristics, safety and efficacy endpoints will be summarized descriptively by dose group and for all subjects combined. Continuous efficacy endpoints will be summarized and may be analyzed using appropriate parametric or nonparametric inference tests. Serum concentrations of QR-110 will be summarized by dose level and time point. To determine the PK profile of IVT injections at the different dose levels of QR-110, the following PK parameters will be calculated if sufficient data are available for each dose:
 

• <math>AUC_{0-\infty}</math>: Area under the curve to infinity will be calculated based on the last observed concentration <math>C_{last}</math> (obs) using formula: <math display="block">AUC_{0-\infty} = AUC_{last} + C_{last}(\text{obs})/\lambda_z, \text{ if feasible.}</math>

• <math>AUC_{0-t_{last}}</math>: Area under the curve to the final sample with a concentration greater than lower limit of quantification (LLOQ) will be calculated based on the last observed concentration using the linear trapezoidal method.

• <math>C_{max}, C_0</math>: The maximum and minimum serum concentrations will be taken directly from the data.

• <math>T_{max}</math>: Time to <math>C_{max}</math> will be taken directly from the data.

• <math>T_{1/2}</math> (if measurable serum levels are obtained): The terminal elimination half-life will be estimated by non-linear regression analysis of the terminal elimination slope, if feasible.

• <math>CL</math>: Serum clearance will be estimated using the formula: <math>CL = \text{Dose}/AUC_{0-\infty}</math>.

• <math>V_d</math> (if measurable serum levels are obtained and an elimination rate constant (<math>\lambda_z</math>) is estimable): Apparent volume of distribution at steady state of the drug will be determined from trough levels.

 
Any p values that will be calculated according to the analysis plan will be interpreted in view of the exploratory nature of the study. Details on statistical analyses will be included in the Statistical Analysis Plan.

-----------------------------	---

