## 8.8 Ophthalmic Exams

Ophthalmic examinations will be performed at all study visits. BCVA will also be assessed at specified time points as indicated per the SOE. The ophthalmic exam is comprised of: BCVA; anterior segment examination, including grading of anterior chamber inflammation according to the Standardization of Uveitis Nomenclature (SUN) Working Group Grading Scheme for Anterior Chamber Flare; IOP; clinical lens grading using the Age-Related Eye Diseases Study (AREDS) Clinical Lens Grading System (ARLNS); posterior segment/fundus examination including grading inflammation in the vitreous using the National Institute of Health (NIH) Grading Scale for Vitreous Haze.

The procedures for ophthalmic exams are outlined in the Study Reference Manual.

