12.1.1 Adverse Events of Special Interest (AESI)

12.2 Slit-Lamp Biomicroscopy Examination

A slit-lamp biomicroscopy examination of the cornea, conjunctiva (palpebral and bulbar), anterior chamber including flare, iris, lens including nuclear, cortical and posterior subcapsular cataract opacity scores, and eyelid/lashes will be performed according to the ocular exam detailed in Section 3.5 of the SAP. The results will be graded as normal, abnormal not clinically significant (NCS) or abnormal clinically significant (CS) with flare scores ranging from 0 to 4+ in whole number increments and lens opacity scores ranging from <1 to >3 in half-point increments.

The results will be summarized using counts and percentages for each dose group and for all subjects for each eye (treated eye and contralateral eye). Tables with percentages will be based on the number of subjects in each dose group with responses. A subject listing of the slit-lamp biomicroscopy parameters will also be produced including the AESIs related to anterior chamber flare and lens opacities.

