12.2.1 Anterior Chamber Flare

Anterior chamber flare will be graded according to the SUN Working Group Grading Scheme using a 5-unit scale where 0 = None, 1+ = Faint, 2+ = Moderate (iris and lens details clear), 3+ = Marked (iris and lens details hazy) and 4+ = Intense (fibrin or plastic aqueous). Anterior chamber flare grade at each visit and change from baseline will be tabulated using continuous and discrete summary statistics.

AESI related to anterior chamber flare will include those TEAEs with MedDRA PT of 'Flare', as described in . The onset date of each reported AESI will be compared to dates of slit lamp biomicroscopy results, and exams with dates between the onset date and resolution of the corresponding AESI will be flagged as having led to an AESI report. The incidence of AESI related to lens opacities will be included in the aforementioned discrete summary by visit.

AESIs related to anterior chamber flare will also be summarized with counts and percentages for each dose group and cohort with the definition of the anterior chamber flare related AESI according to Section 13.1.1 of the SAP. AESI related to anterior chamber flare will include those TEAEs with MedDRA PT of 'flare'. In order to establish if results at individual visits resulted in an AESI report or not, the onset date of each reported AESI related to anterior chamber flare will be compared to dates of slit lamp biomicroscopy results, and exams with dates between the onset date and resolution of the corresponding AESI will be flagged as having led to an AESI report.

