12.2.2 Lens Opacity Examination

Clinical lens opacities will be graded using the Age-Related Eye Diseases Study (AREDS) protocol and the Clinical Lens Grading System (ARLNS) on a 7-unit scale from <1 to >3 with half unit increments. . Lens nuclear opacity, cortical opacity and PSC opacity and changes from baseline summarized using continuous and discrete descriptive statistics.

AESIs related to lens opacities will also be summarized with counts and percentages for each dose group and cohort with the definition of the lens opacity related AESI according to Section 13.1.1 of the SAP. AESI related to lens opacities will include those TEAEs with MedDRA PT of 'eye opacity'. In order to establish if results at individual visits resulted in an AESI report or not, the onset date of each reported AESI related to lens opacities will be compared to dates of slit lamp biomicroscopy results, and exams with dates between the onset date and resolution of the corresponding AESI will be flagged as having led to an AESI report.

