12.3 Posterior Segment/Fundus Examination

A posterior segment/fundus examination of the vitreous, macula, optic nerve, peripheral retina and choroid will be performed at each visit. The results will be graded as normal, abnormal NCS or abnormal CS. Vitreous haze is also assessed with possible scores of 0, 0.5+, 1+, 2+, 3+, or 4+. Cup-to-Disc ratio is also assessed in the Posterior Segment/Fundus Examination on a 0.1 to 1.0 scale in increasing increments of 0.1.

The results will be summarized using counts and percentages for each dose group and for all subjects at each visit for each eye (treated eye and contralateral eye). Percentages will be based on the number of subjects in each dose group with responses. AESI will also be summarized with counts and percentages for each dose group and cohort with the definition of the vitreous haze related AESIs according to Section 12.1.1 of the SAP. A subject listing of the posterior segment/fundus examination parameters will also be produced. Vitreous haze related AESI will include those TEAEs with MedDRA PT of 'vitreous haze'. In order to establish if results at individual visits resulted in an AESI report or not, the onset date of each reported AESI related to lens opacities will be compared to dates of fundus exam results, and exams with dates between the onset date and resolution of the corresponding AESI will be flagged as having led to an AESI report.

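### SAP 12.2 and 12.3 plan no within-eye change for slit-lamp structure grades or the fundus examination, so where eyes enter abnormal the tables cannot show how many worsened

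*Protocol*

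**What the plan says.** Protocol 1.0 and 4.1.2 and SAP 1.5 all list "Changes in ophthalmic examination findings" as a secondary endpoint. None of them defines a metric. Protocol 8.8 sets out the examination: "The ophthalmic exam is comprised of: BCVA; anterior segment examination, including grading of anterior chamber inflammation", followed by IOP, lens grading and a posterior segment examination with a vitreous haze grade. Protocol 10.6.4 leaves the summaries of this examination to the SAP.

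For the slit-lamp structure grades (normal, abnormal NCS, abnormal CS), SAP 12.2 says: "The results will be summarized using counts and percentages for each dose group and for all subjects for each eye". On denominators it adds: "Tables with percentages will be based on the number of subjects in each dose group with responses". For the fundus, SAP 12.3 covers five structures, vitreous haze and cup-to-disc ratio, and says: "The results will be summarized using counts and percentages for each dose group and for all subjects at each visit for each eye". The same denominator rule follows.

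Other parts of the examination are handled differently. On flare, SAP 12.2.1 says: "Anterior chamber flare grade at each visit and change from baseline will be tabulated using continuous and discrete summary statistics". On the lens, SAP 12.2.2 says: "Lens nuclear opacity, cortical opacity and PSC opacity and changes from baseline summarized using continuous and discrete descriptive statistics". SAP 12.4 plans change from baseline for IOP. SAP 14.1 plans change from baseline and category shifts for BCVA.

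**The concern.** The endpoint is a change, but for the slit-lamp structure grades and the whole fundus examination the stated output is a level at a time point. A level answers a different question. An eye that becomes abnormal can be offset in the count by another eye that resolves. An eye with no result leaves the denominator, so the percentage can move although no eye has changed.

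This matters because fundus findings and vitreous haze are among the direct clinical signs of inflammation or retinal harm after an intravitreal injection, in a first-in-human safety study. A reader of the summary tables would want to know how many treated eyes got worse than at entry, and how many contralateral eyes did. For these parts of the examination the tables as specified do not say.

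**Working it through.** No stated figure bears on this point: the endpoint is descriptive and the sample size is not power-based (Protocol 10.2, SAP 4). The check is a comparison of the text, followed by an illustration.

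**Step 1: what is planned for each component.**

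| Component | SAP | Within-eye change stated? |
|---|---|---|
| BCVA | 14.1 | Yes: change and category shift |
| Anterior chamber flare | 12.2.1 | Yes |
| Lens opacity (nuclear, cortical, PSC) | 12.2.2 | Yes |
| IOP | 12.4 | Yes |
| Slit-lamp normal/NCS/CS grades | 12.2 | No |
| Fundus structure grades | 12.3 | No |
| Vitreous haze | 12.3 | No |
| Cup-to-disc ratio | 12.3 | No |

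SAP 7.3 names slit lamp and fundus among the measures whose baseline is the final reading before the first dose. The last four rows never use that baseline. SAP 7.4 explains how a change is computed (follow-up minus baseline), but it does not say that one is tabulated here. Normal/NCS/CS grades cannot be subtracted; they need a shift table.

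**Step 2: what visit counts can reveal.** Let n be the eyes seen at both times, b the number abnormal at baseline, v the number abnormal at the visit, w the newly abnormal eyes and r the resolved eyes. Then v = b − r + w. If v = b, then w = r. Since w ≤ n − b and r ≤ b, w can be any whole number from 0 to min(b, n − b).

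Inputs: SAP 7.6 gives 11 subjects at interim analysis 2, and SAP 3 gives two dose groups. The split between groups is not given. Group sizes of 4, 5 and 6 and all values of b are therefore assumptions.

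- n = 6, b = v = 2 (2/6 = 33.3% both times): w from 0 to min(2, 4) = 2, out of 4 eyes at risk.
- n = 6, b = v = 3: w from 0 to min(3, 3) = 3, out of 3 at risk.
- n = 5, b = v = 2 or 3: w from 0 to 2.
- n = 4, b = v = 2: w from 0 to 2.
- n = 11 (all subjects), b = v = 5 or 6: w from 0 to 5.
- b = 0: every abnormal eye at the visit is new, and nothing is masked among the eyes seen.

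**Step 3: a missing eye.** Start from 2/6 = 33.3% and lose one eye.

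- If the lost eye is one of the two abnormal eyes and no other eye changes, the table reads 1/5 = 20.0%, an apparent improvement with no eye improved.
- Without knowing which eye was lost, 2/6 followed by 1/5 fits 0 or 1 newly abnormal eye, and 2/6 followed by 2/5 (40.0%) fits 0 to 2.

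**The case against.** The strongest reply is that little is lost in practice. SAP 7.4 lists all data by subject, eye and visit, and 12.2 and 12.3 add their own listings. With 11 subjects a reviewer can read each eye. Worsening that the investigator judges to be an adverse event is reported as one, and ocular adverse events by eye are the primary endpoint. SD-OCT and NIRAF have change from baseline (SAP 14.6, 14.7). Eligibility requires clear ocular media (Protocol 5.3.1), so few eyes should enter with vitreous haze. Protocol 2.3 describes a fairly normal optic disc and a relatively preserved posterior pole, so b may be small for some structures. An eye that enters as abnormal CS is already at the top of the scale, and a shift table cannot show it worsening either. Finally, the table shells are not visible, and the SAP revision history records that one shift table was produced before the text described it.

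Most of this stands, and it limits the point. A reader might infer that the whole examination lacks change analyses, or that worsening eyes would go unseen. The documents support neither: four measured components have change analyses, and masking is confined to the summary tables. Masking of haze in particular is less likely than for retinal structures, where Protocol 2.3 also describes progressive degeneration and loss of peripheral rods.

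The core gap is not answered. A listing is not a summary of a named endpoint. Adverse event reporting depends on a judgement that a shift table does not need. The AESI flagging in SAP 12.3 starts from an event already reported and covers haze only; its linking sentence also refers to lens opacities instead of haze.

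**Conclusion.** The point holds for the slit-lamp normal/NCS/CS grades and for the fundus examination (structure grades, vitreous haze, cup-to-disc ratio). For these, the planned tables do not deliver the within-eye change that the endpoint names, and where eyes are abnormal at baseline the number that worsened cannot be recovered from the tables. The fault lies in SAP 12.2 and 12.3, not in the protocol's endpoint line.

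The size depends on how many eyes are abnormal at entry, which the documents do not give. Under the assumed group of 6 with unchanged totals, the uncertainty runs from none (b = 0) to 3 eyes (b = 3). The conclusion also rests on the SAP text as published. If the table shells already contain these shifts, only the wording is missing. This is a worthwhile correction to a descriptive safety summary; it does not undermine the primary endpoint.

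**What to change.** In SAP 12.2 and 12.3:

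- Add a within-eye shift (normal / abnormal NCS / abnormal CS) from the SAP 7.3 baseline to the worst post-baseline grade and to each visit, by treated and contralateral eye and by dose group, with a missing column, for each slit-lamp and fundus structure.
- Add the same shift for vitreous haze grade.
- Add a change-from-baseline summary for cup-to-disc ratio.
- Report the number of eyes that worsen by at least one grade over the number at risk, meaning eyes not already at the top grade at baseline.

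The same shift can be applied to physical examination (SAP 12.5), where the endpoint is likewise a change and only counts and percentages are planned.

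No new assessments are needed. The format already exists in the plan: SAP 14.1 for vision category and Protocol 10.6.3 for laboratory values. The cost is SAP wording, programming and a number of sparse tables, more if each is split by adult and pediatric cohort. Making the worst-post-baseline shift the main table, with the by-visit shifts as supporting output, keeps that in check.
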